## **6. DESIGN OF THE CLINICAL INVESTIGATION**

### **6.1 GENERAL**

#### **6.1.1 Type of Clinical Investigation and Rationale**

Study GX28228 is a Phase II, multicenter, randomized, active treatment (monthly ITV injection)–controlled study to evaluate ranibizumab delivered through the Implant using three ranibizumab formulation arms (10 mg/mL, 40 mg/mL, and 100 mg/mL) compared with the control arm (0.5-mg monthly ITV injections of 10-mg/mL formulation) in patients with subfoveal neovascular (wet) AMD.

For details of the rationale for the design, refer to the Phase II protocol Section 3.4.

## **Appendix 21**

### **Ranibizumab Port Delivery System: Device Clinical Investigation Plan (cont.)**

#### **6.1.2           Measures to Minimize or Avoid Bias**

Patients will be randomized through an interactive voice/Web response system to one of four treatment arms.

Study patients and all study site personnel will be masked to the Implant treatment arms' ranibizumab formulation assignment (10 mg/mL vs. 40 mg/mL vs. 100 mg/mL) until the study conclusion.

The Sponsor's personnel directly involved in the study conduct (except the Internal Monitoring Committee [IMC] members) will be masked to the Implant treatment arms' ranibizumab formulation assignment (10 mg/mL vs. 40 mg/mL vs. 100 mg/mL) until the time of primary analyses. The IMC will closely monitor patient safety throughout the study (see protocol Section 3.1.4). The IMC roles and responsibilities will be outlined in the IMC charter.

Clinical pharmacology and PK scientists may be unmasked early for the purposes of interpreting emerging safety and efficacy data; those unmasked staff will not be part of the study team or have any interactions with sites or investigators.

In addition, the VA examiner will only conduct refraction and VA assessments and will be masked to patient study eye assignment and patient treatment assignment. The VA examiner will have no access to patient VA scores from previous visits but will be only aware of the patient's refraction data from previous visits. The VA examiner may perform no other direct patient-care tasks. Patients will be asked not to discuss their study eye assignment (right versus left) with the VA examiner.

Patients and study site personnel will not be masked with regard to patient assignment to the ITV arm or an Implant arm because of the difficulties of maintaining masking following the surgical procedure, the additional safety visits applicable only to the Implant arms, and Implant visualization upon ophthalmic examination.

#### **6.1.3           Device Endpoints, with Rationale for Their Selection and Measurement**

The Implant endpoint is the Implant status at the end of trial, which will be reported as either clogged or not clogged. The rationale for selecting Implant clogging as an endpoint is described in Section 3 of this RPDS CIP.

## Appendix 21

### Ranibizumab Port Delivery System: Device Clinical Investigation Plan (cont.)

#### **6.1.4 Methods and Timing for Assessing, Recording, and Analyzing Variables**

Details of the assessments to be performed during the study are provided in Appendix 1 of the Phase II protocol. The Implant clogging rate at Month 9 will be determined (see Section 5.3).

#### **6.1.5 Equipment to be Used for Assessing the Clinical Investigation Variables and Arrangements for Monitoring Maintenance and Calibration**

Not applicable.

#### **6.1.6 Procedures for the Replacement of Subjects**

Patients who discontinue from the study will not be replaced.

### **6.2 INVESTIGATIONAL DEVICE(S) AND COMPARATOR(S)**

#### **6.2.1 Description of the Exposure to the Investigational Device(s) or Comparator(s), If Used**

##### **Patients in the Implant Treatment Arms**

Patients will have the Implant (prefilled with approximately 20  $\mu$ L of either the 10-mg/mL [approximately 0.2 mg dose], 40-mg/mL [approximately 0.8 mg dose], or 100-mg/mL formulation [approximately 2 mg dose] of ranibizumab) surgically inserted in the study eye at the Day 1 visit. For further details regarding exposure, refer to protocol Section 4.3.2.2.

##### **Patients in the ITV Injection Treatment (Control) Arm**

Patients will receive their first ITV injection of 50  $\mu$ L of the 10-mg/mL ranibizumab (0.5 mg dose) formulation at the Day 1 visit. For further details regarding exposure, refer to protocol Section 4.3.2.2.

#### **6.2.2 Justification of the Choice of Comparator(s)**

Refer to details in protocol Section 3.4.4.

#### **6.2.3 List of Any Other Medical Device or Medication to be Used During the Clinical Investigation**

No medical devices other than the RPDS or medication for the treatment of neovascular AMD in the study eye will be used during the clinical investigation.

#### **6.2.4 Number of Investigational Devices to be Used**

One Implant per study eye will be used during the clinical investigation in patients randomized to the RPDS treatment arms.

## Appendix 21

### Ranibizumab Port Delivery System: Device Clinical Investigation Plan (cont.)

#### 6.3 SUBJECTS

##### 6.3.1 Inclusion Criteria for Subject Selection

Patients with choroidal neovascularization secondary to AMD will be enrolled in the study. Written informed consent will be obtained before initiation of any study-related procedures.

For the complete list of inclusion criteria, refer to protocol Section 4.1.1.

##### 6.3.2 Exclusion Criteria for Subject Selection

For the complete list of exclusion criteria, refer to protocol Section 4.1.2.

No additional exclusions may be applied by the investigator, in order to ensure that the study population will be representative of all eligible patients.

##### 6.3.3 Criteria and Procedures for Subject Withdrawal or Discontinuation

Patients have the right to voluntarily withdraw from the study at any time for any reason. In addition, the investigator has the right to withdraw a patient from the study at any time. For details, refer to protocol Section 4.7.1.

Discontinued patients will not be allowed to re-enter the study.

##### 6.3.4 Point of Enrollment

The study will include pre-screening (if applicable), “run-in” (if applicable), screening, and randomization visits followed by a treatment period. Subjects will be enrolled into the study at the office of their vitreo-retinal specialist. Patients randomized to the Implant treatment arms will have the Implant (pre-filled with ranibizumab) surgically inserted in the study eye at their Day 1 visit.

For additional details regarding description of study, refer to protocol Section 3.1.

##### 6.3.5 Total Expected Duration of the Clinical Investigation

Approximately 220 patients will be randomized within an approximate 24-month period of time. It is expected that the duration of the clinical investigation (length of study plus enrollment period) will be approximately 38 months.

##### 6.3.6 Expected Duration of Each Subject's Participation

Patients in the ITV injection arm *will be evaluated monthly and will receive monthly study treatments (Day 1, Month 1 through Month X visit, see protocol Appendix 2) until the Sponsor decides, based on the primary analysis results, to either terminate the*

## **Appendix 21**

### **Ranibizumab Port Delivery System: Device Clinical Investigation Plan (cont.)**

*study and discontinue study treatment, or offer patients entry into the RPDS Extension Study.* Their participation (excluding screening period) in the study will last approximately 13–38 months dependent on the date of their randomization to the study.

The patients in the Implant arms will continue to be evaluated monthly for the Implant refill (see protocol Appendix 1) until the Sponsor decides, based on the primary analysis results, to either terminate the study and discontinue study treatment, or offer patients entry into the RPDS *Extension Study*. The Implant arms patients' study participation (excluding screening period) is expected to last approximately 13 to 38 months dependent on the date of their randomization to the study.

#### **6.3.7 Number of Subjects Required to be Included in the Clinical Investigation**

Approximately 220 patients up to 60 sites in the United States will be randomized in a 3:3:3:2 ratio to four treatment arms: approximately 60 patients will receive the Implant filled with 10-mg/mL ranibizumab formulation, 60 patients will receive the Implant filled with 40-mg/mL ranibizumab formulation, 60 patients will receive the Implant filled with 100-mg/mL ranibizumab formulation, and 40 patients will receive monthly ITV injections of 10-mg/mL ranibizumab formulation (50 µL for the 0.5-mg dose).

#### **6.3.8 Estimated Time Needed to Select this Number (i.e., Enrolment Period)**

The enrolment period is expected to be approximately 24 months.

### **6.4 PROCEDURES**

For details regarding post-trial access to treatment, refer to protocol Section 4.4.2.

#### **6.4.1 Description of All the Clinical-investigation-related Procedures that Subjects Undergo During the Clinical Investigation**

Medical history and demographic information will be collected.

Medical history includes clinically significant diseases, surgeries, smoking history, and use of alcohol.

All medications other than protocol-specified procedural medications used by the patient within 7 days prior to the randomization visit until the study completion will be recorded on the electronic case report form (eCRF) concomitant medication log.

Demographic data will include age, sex, and self-reported race/ethnicity.

## **Appendix 21**

### **Ranibizumab Port Delivery System: Device Clinical Investigation Plan (cont.)**

The Implant insertion and explantation procedures will be captured on video for Investigators' training purposes unless the study center has policies in place that prohibit these procedures being captured by video. The Implant refill procedure video capture is optional.

For a complete list of study assessments, refer to protocol Section 4.6.

Please see the schedule of assessments provided in protocol Appendix 1 and Appendix 2 for the schedule of assessments to be performed at each study visit.

#### **6.4.2 Description of Those Activities Performed by Sponsor Representatives (Excluding Monitoring)**

Genentech and/or its designee will perform study management, oversight of data management, statistical programming, project management, monitoring, vendor management, and data management (quality checking of the data).

For additional details regarding administrative structure, refer to protocol Section 9.4.

#### **6.4.3 Any Known or Foreseeable Factors That May Compromise the Outcome of the Clinical Investigation or the Interpretation of Results**

Not applicable.

#### **6.4.4 Monitoring Plan**

Study monitors will perform ongoing source data verification to confirm that critical protocol data (i.e., source data) entered into the eCRFs by authorized site personnel are accurate, complete, and verifiable from source documents. Refer to protocol Section 7.4 for additional details regarding source data documentation.

### **7. STATISTICAL CONSIDERATIONS**

#### **7.1 STATISTICAL DESIGN, METHOD AND ANALYTICAL PROCEDURES**

One objective in the clinical study is to demonstrate that there is no evidence that the Implant clogging rate exceeds 10% of patients in the Implant arms at Month 9.

Implant clogging data from all patients that receive the Implant will be pooled together for this analysis. If there are 22 or fewer clogged Implants, among 165 evaluable Implants, within 9 months since insertion, we can declare that there is no evidence for the initial Implant clogging rate exceeding 10%. This acceptance criterion will be adjusted based on the actual number of evaluable Implants at end of study. The proportion of Implants

## Appendix 21

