#### **6.4.2 Secondary Efficacy Analysis**

A secondary efficacy outcome measure is the change in BCVA from baseline through Month 9 (by month). Missing BCVA data, prior to or at Month 9 for each patient, will be imputed using the last observation carry forward (LOCF). Comparison of implant arms (10 mg/mL, 40 mg/mL, and 100 mg/mL) versus the monthly ITV arm will be assessed using an analysis of covariance (ANCOVA) model with an effect for treatment and with covariate adjustments for baseline stratification factors: baseline BCVA score ( $\leq 65$  letters vs.  $\geq 66$  letters) and number of anti-VEGF ITV injections ( $\leq 3$  vs.  $\geq 4$ ). Separate models will be fit for each pairwise comparison and each study month. The dependent variables will be change from baseline in BCVA at each of Months 1–9. Model-based (least squares) estimates of the pairwise treatment differences will be provided and 80% CIs. Figures showing mean and median change in BCVA over time, by treatment group, will be provided.

The ANCOVA model above will be repeated using change from baseline in CFT from baseline through Month 9 (by month) as the outcome. The stratification factors and baseline CFT will be included in the model as covariates. Mean change from baseline in CFT from baseline through Month 9 (by month) will be compared between the implant arms and the monthly ITV arm.

In order to evaluate whether the Implant clogging rate exceeds 10% within the first 9 months, the proportion of clogged Implants will be estimated and the 80% CI will be calculated based on the binomial distribution. All clogging data from patients in the implant arms will be pooled for this analysis.

Additional statistical summaries will be reported for the secondary efficacy outcome measures as listed in Section 3.5.2. Detailed specifications of the statistical methods will be described in the SAP.

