### Ranibizumab Port Delivery System: Device Clinical Investigation Plan (cont.)

that clog within 9 months and its 90% confidence interval will be estimated based on the binomial distribution.

In addition, the safety data from three Implant arms will be pooled and compared with monthly ITV injection arm. The summary statistics (frequency and percentage) will be provided by Implant arm and monthly ITV arm. The safety assessment will review the following:

- AEs
- SAEs
- “Prespecified RPDS-associated AEs” (see protocol Section 6.5.1)

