#### 7.2 SAMPLE SIZE

This study is exploratory in nature and designed to estimate the time to first refill (TTFR) for each of the RPDS treatment arms (10 mg/mL, 40 mg/mL, and 100 mg/mL) enrolling 60 patients in each of the RPDS treatment arms. The sample size of approximately 220 randomized patients will be *adequate* to evaluate the primary objective of the study. Pharmacokinetic-Pharmacodynamic modeling and simulation was performed to inform key assumptions used in sample size calculation. *Given* the simulation results, the hazard ratio for comparing the 100-mg/mL arm to the 10-mg/mL arm was estimated to be 0.66 for TTFR. *Assuming this hazard ratio, a total of at least 125 events from all three Implant groups is expected at the primary analysis time (approximately 85 events in the 10-mg/mL group and a higher dose group). With 85 events, this study will have approximately 80% power to detect a hazard ratio=0.66 between the two Implant arms using a log-rank test at a one-sided significance level of 15%. No multiplicity adjustment is planned for this Phase II study.*

Forty patients in the ITV arm will be sufficient to compare each device arm versus the ITV arm in change in BCVA from baseline through Month 9 (assuming an estimated SD=10 letters, a two-sided 80% CI will extend approximately 2.62 letters from the observed mean).

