#### 7.3 THE LEVEL OF SIGNIFICANCE AND THE POWER OF THE DEVICE CLINICAL INVESTIGATION

The significance level used for Implant clogging data analysis is 0.05 and a one-sided test will be performed. 80% statistical power was used in above sample size section.

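### The 80% power cited for the device investigation belongs to the time-to-first-refill test, and the clogging limit of 22 of 165 holds one-sided 5% only under an uncorrected normal approximation (exact level 6.5%).

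*Protocol*

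**What the plan says.** The device objective in CIP 7.1 is to show that "there is no evidence that the Implant clogging rate exceeds 10% of patients in the Implant arms at Month 9". The decision rule is a count: "22 or fewer clogged Implants, among 165 evaluable Implants" within 9 months of insertion. The limit is to be adjusted to the number of implants actually evaluable, but no formula is given. The same section says that the proportion of implants "that clog within 9 months and its 90% confidence interval will be estimated based on the binomial distribution"; CIP 5.2 also gives 90%.

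CIP 7.3, headed as the level and power of the device investigation, reads: "The significance level used for Implant clogging data analysis is 0.05 and a one-sided test will be performed". It then adds: "80% statistical power was used in above sample size section". The test is not named.

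CIP 7.2 contains one power statement: "approximately 80% power to detect a hazard ratio=0.66 between the two Implant arms using a log-rank test at a one-sided significance level of 15" (per cent), based on "approximately 85 events in the 10-mg/mL group and a higher dose group". CIP 7.4 says that an 8% dropout rate was assumed in the sample size section for the clogging analysis.

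Two other places bear on the same proportion. Protocol 6.4.2 says "the 80% CI will be calculated based on the binomial distribution". SAP 4.4 defaults to 95% intervals and plans no tests except for the primary endpoint, and SAP 1 and 2.1 say that the SAP supersedes the protocol's analysis plan.

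**The concern.** A reader of CIP 7.3 would take the 80% as the chance that the clogging rule detects a device that clogs too often. If the figure belongs to another endpoint, the device test has no stated power at all.

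The limit itself also needs checking against the stated 5% level, because CIP 7.1 names the binomial distribution for the interval and a count of 23 falls close to the boundary.

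The consequences are practical. CIP 7.5 makes clogging a formal pass/fail objective and mandates design changes if the objectives are not met. CIP 1 says that the plan will support a CE certificate.

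**Working it through.** **Inputs.** n = 165, pass at 22 or fewer, null rate 10% (CIP 7.1); one-sided 0.05 (7.3); 3 × 60 = 180 implant patients, 85 events, HR 0.66, one-sided 15% (7.2); 8% dropout (7.4).

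**Where 165 comes from.** 180 × (1 − 0.08) = 165.6. The number is consistent with 7.4, but 7.2 shows neither the dropout rate nor this step.

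**What the 80% is.** By the Schoenfeld formula with equal allocation, power = Φ(|ln 0.66| × √85 / 2 − 1.036) = Φ(0.4155 × 4.610 − 1.036) = Φ(0.879) = 0.810. This reproduces the stated figure for TTFR. Nothing in 7.2 yields a clogging power, because no alternative clogging rate is given.

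**Reproducing the limit.** With the z test, null variance and no continuity correction: 165 × 0.10 + 1.645 × √(165 × 0.10 × 0.90) = 16.5 + 1.645 × 3.854 = 22.84, so pass at 22. At 23 clogged, z = 6.5 / 3.854 = 1.687 and one-sided p = 0.0458. The Wilson 90% lower bound at 23 is 10.08%, which agrees.

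**Exact level.** For X ~ Binomial(165, 0.10):

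| Clogged | P(X ≥ count) | Exact 90% lower bound |
|---|---|---|
| 22 | 0.1005 | 9.20% |
| 23 | 0.0647 | 9.72% |
| 24 | 0.0399 | 10.24% |
| 25 | 0.0237 | 10.76% |

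The rule fails the device at 23 or more, so its exact level is 6.5%. An exact test at 5% would pass 23 and fail at 24 (level 4.0%). At 23 of 165 the exact 90% interval is 9.7% to 19.2%, so it does not exclude 10%.

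**Interval levels.** An exact interval excludes 10% from below once the tail probability drops under half its non-coverage. From the table, the largest count that still includes 10% is 22 with an 80% interval (0.1005 against 0.10), 23 with 90% (0.0647 against 0.05) and 24 with 95% (0.0399 against 0.025). The three levels in the documents therefore imply three different limits.

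**Adjustment to the actual n.** The choice of method matters at some sizes and not at others. The z and exact limits are 22 and 22 at n = 159, 22 and 23 at 165, 23 and 23 at 168, and 23 and 24 at 171.

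**Operating characteristics.** The true rates below are my assumptions, because the documents give none. The entries are the exact probability of failing the device.

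| True rate | Limit 22 | Limit 23 |
|---|---|---|
| 12% | 25% | 19% |
| 13% | 39% | 31% |
| 14% | 54% | 45% |
| 15% | 68% | 60% |
| 16% | 79% | 73% |

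With limit 22, 80% is reached at a true rate of about 16.1%.

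**The case against.** The strongest reply is that 22 is not a mistake. CIP 7.3 names no test, and a standard one-sided 5% z test gives exactly this limit. A reader might infer from the exact 6.5% that the limit was miscalculated or simply lacks its stated level. The documents do not support that: the limit is correct for an approximation that is somewhat liberal here. Likewise, 7.1 asks for an interval based on the binomial distribution without saying which. The Wilson interval agrees with the count rule at 23; the exact interval does not. The disagreement is therefore a consequence of an unnamed method, not a proven contradiction.

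A reader might also infer that the limit should move to 23. That does not follow. The gap is one implant, and 22 is the stricter choice. A limit of 23 would pass a device with a true 15% clogging rate 40% of the time instead of 32%, and one at 12% about 81% instead of 75%.

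Finally, it is tempting to say that the trial was presented as sized for clogging. CIP 3 says openly that the design and sample size aim at the dosing regimen, and 7.2 ties its 80% to the hazard ratio. That limits the harm, but it does not rescue 7.3: under a heading about the power of the device investigation, the sentence points to a calculation that is not there, and 7.4 repeats the fault for dropout.

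**Conclusion.** The power point holds in full. The only 80% in CIP 7.2 is the TTFR log-rank power at one-sided 15%, and no clogging power can be derived from the documents.

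The level point holds in a limited form. The rule meets 5% only under the uncorrected normal approximation; exactly, it runs at 6.5%. The difference is one implant, and its direction is to fail a device at a true 10% slightly too often. The exact figures assume independent implants with a common clogging probability and n = 165. The actual n may differ, both through the adjustment promised in CIP 7.1 and because SAP 4.1 excludes a non-compliant site from the efficacy analyses.

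The status of the analysis is also unsettled: 90%, 80% and 95% intervals could each be read as applying, and the SAP's rule against tests beyond the primary endpoint sits beside a one-sided test in the CIP.

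**What to change.** - **CIP 7.1:** keep the limit of 22. State the method that produced it, its exact level (6.5% at n = 165), and the same method as the rule for adjusting it to the actual number of evaluable implants. If an exact 5% test is preferred, the limit is 23 (level 4.0%), and the higher chance of passing a clogging device should be stated with it.
- **CIP 7.3:** delete the 80% sentence. Say that the trial was not sized for clogging, and give the chance of failing the device at assumed true rates, labelled as illustrations: about 25% at 12%, 39% at 13%, 68% at 15% and 79% at 16%. The 16% rate should not be presented as a design assumption.
- **CIP 7.4:** correct the cross-reference, for example by showing 180 × 0.92 = 165.6 where the 8% is used.
- **CIP 5.2 and 7.1, protocol 6.4.2 and SAP 4.4:** choose one interval level and type for clogging, and say whether the clogging rule is a formal test or a descriptive criterion.

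The cost is text only, with no change to sample size or conduct. The downside is that the stated properties of the device test become less favourable.
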